9.5 Physical Examination Data

By-patient listings will be provided for physical examination.

9.6 Electrocardiogram Data

Electrocardiogram (ECG) data will not be summarized since ECG data will be collected at the screening visit only.

10 Pharmacodynamic Analyses

Urinary excretions will be determined as urine concentration \times urine volume; missing values will not be imputed. If urine concentration or volume is missing for any interval, the 0 to 24 hour values will not be determined. Urine volumes of zero, and consequently non reportable urine concentration, are not considered as missing data; values of 0 will be reported for volume and excretion.

Free water clearance will be determined as urine excretion rate – osmolar clearance.

Osmolar, sodium, and creatinine clearances will be determined by standard methods with average serum concentration determined by averaging the concentrations at the beginning and end of the urine collection interval. If urine volume for a collection interval is 0, then the clearance value for that interval and the following interval will be determined by using the average value of the 3 serum concentrations, the urine volume of the second interval and the total time of the 2 collection intervals (eg, 2 to 4 hour collection has urine volume of 0 mL). Clearance for the 2 to 4 and 4 to 8 hour intervals will be determined using serum concentrations at 2, 4, and 8 hours, the urine volume from 4 to 8 hour interval and total collection time of 6 hours (8 minus 2).

Values of urine osmolality will be summarized with descriptive statistics by total daily dose (all placebos grouped together) and collection interval. Sodium and creatinine urine concentrations will only be listed.

Protocol 156-12-298

Values of excretions (osmoles, sodium, and creatinine) and clearances (free water, sodium, and creatinine) will be summarized with descriptive statistics by total daily dose (all placebos grouped together), collection interval, and 0 to 24 hours.

Serum concentrations (osmolality, sodium, and creatinine) and change from predose will be summarized with descriptive statistics by total daily dose (all placebos grouped together), analyte, and time point.

11 Interim Analysis

No interim analysis is planned before all randomized subjects either complete the Month 12 visit or early terminate in Phase A, the double-blind, placebo-controlled portion of this protocol. A snapshot of the database will be taken after all subjects in Phase A have completed or early terminated, these data will be unblinded, and an interim CSR will be written to provide early information on safety.

12 Monitoring of Safety Data

12.1 Independent Data Monitoring Committee

An independent data monitoring committee (IDMC) will be established for this trial. This committee will meet on a regular basis to ensure the safe and ethical treatment of trial subjects, ensure the scientific integrity of the trial, and to ensure the trial is conducted within the bounds of ethical medical practice. It may make recommendations to the sponsor and trial steering committee to amend or terminate the trial based on grounds of safety, futility, or greater than expected efficacy as defined by the accepted statistical practices and procedures to be detailed in their charter. The specific duties of the IDMC will be detailed in a separate IDMC charter document.

12.2 Hepatic Adjudication Committee

A hepatic adjudication committee (HAC) has been convened for the purpose of oversight of hepatic events. The HAC will independently determine probable cause(s) of any hepatic event occurring during the trial and will communicate with the IDMC that oversees the trial.

Protocol 156-12-298

13 References

- ¹ Schwartz G, Munoz A, Schneider M, Mak R, Kaskel F, Warady B et al. New equations to estimate GFR in children with CKD. *J Am Soc Nephrol*. 2009;20(3):629-37.
- ² Guidance for Industry, Drug-Induced Liver Injury: Premarketing Clinical Evaluation. US Department of Health and Human Services, Food and Drug Administration, and Center for Drug Evaluation and Research (CDER), July 2009.

Protocol 156-12-298

14 Appendices

Appendix 1: Criteria of Potentially Clinically Significant Laboratory Test Abnormalities

Laboratory Test Abnormalities due to Test Value Increase

Test	Abnormality	Test Result Grade				
		0	1	2	3	4
APTT (sec)	Increase	ULN	>ULN - 1.5xULN	>1.5xULN - 2xULN	>2xULN	
ALT (SGPT) (IU/L)	Increase	ULN	>ULN - 3xULN	>3xULN - 5xULN	>5xULN - 20xULN	>20xULN
AST (SGOT) (IU/L)	Increase	ULN	>ULN - 3xULN	>3xULN - 5xULN	>5xULN - 20xULN	>20xULN
Bilirubin, Total (mg/dL)	Increase	ULN	>ULN - 2xULN	>2xULN - 3xULN	>3xULN - 10xULN	>10xULN
Creatinine (mg/dL)	Increase	B*	>B - 1.5xB	>1.5 x B - 3 x B	> 3 x B - 6 x B	> 6 x B
Eosinophils, Absolute (Thous/ μ L)	Increase	≤ 0.65	>0.65-1.5	>1.5-5	>5	
Glucose (mg/dL)	Increase	≤ 115	>115-160	>160-250	>250-500	>500
Hemoglobin (g/dL)	Increase	ULN	>ULN-20	>20-21	>21-22.5	>22.5
Potassium (mEq/L)	Increase	ULN	>ULN-5.5	>5.5-6	>6-7	>7
INR	Increase	ULN	>ULN - 1.5xULN	>1.5xULN - 2xULN	>2xULN	
Sodium (mg/dL)	Increase	<145	146 - 150	151 - 155	156 - 160	>160
Triglycerides (mg/dL)	Increase	ULN	>ULN - 2.5xULN	>2.5xULN - 5xULN	>5xULN - 6xULN	>6xULN
Urea Nitrogen (mg/dL)	Increase	≤ 22	>22-26	>26-31	>31	
White Blood Count (Thous/ μ L)	Increase	≤ 10.79	>10.79-15	>15-20	>20-25	>25

*B= Baseline

Laboratory Test Abnormalities due to Test Value Decrease

Test	Abnormality	Test Result Grade				
		-4	-3	-2	-1	0
Glucose (mg/dL)	Decrease	<30	30-<40	40-<55	55-<65	≥ 65
Hemoglobin (g/dL)	Decrease	<6.5	6.5-<8	8-<10	10-<LLN	LLN
Lymphocytes, Absolute (Thous/ μ L)	Decrease	<0.2	0.2-<0.5	0.5-<0.8	0.8-<LLN	LLN
Neutrophils, Absolute (Thous/ μ L)	Decrease	<0.5	0.5-<1	1-<1.5	1.5-<LLN	LLN
Platelet Count	Decrease	<25	25-<50	50-<75	75-<LLN	LLN

Protocol 156-12-298

Test	Abnormality	Test Result Grade				
		-4	-3	-2	-1	0
(Thous/ μ L)						
Potassium (mEq/L)	Decrease	<2.5	2.5-<3		3-<LLN	LLN
Sodium (mg/dL)	Decrease	<120	120-124	125-129	130-135	\geq 136
White Blood Count (Thous/ μ L)	Decrease	<1	1-<1.5	1.5-<2.5	2.5-<3.501	\geq 3.501

Protocol 156-12-298

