1.3 Known and Potential Risks and Benefits

ADPKD is a devastating, progressive disease that places a tremendous burden on patients and their families. The risk which a patient is willing to accept is a personal decision based on his/her individual and familial experience with the disease.

The most common observed risks of tolvaptan therapy in adults include those arising from aquaresis (eg, polyuria, pollakiuria, nocturia, thirst, dry mouth), dehydration, electrolyte abnormalities, and gout. While aquaretic events did not contribute to significant subject morbidity over 3 years of study in the pivotal placebo-controlled trial (Trial 156-04-251), they do represent adverse drug reactions which occur early (within days to weeks) and are most likely to limit a subject's ability to continue therapy over a duration of treatment that is likely to provide benefit. While the proposal of increased water ingestion as a mechanism of ameliorating CKD⁹ has not reached medical equipoise, in this trial we believe a general recommendation to do so is reasonable and would recommend ingestion of water adequate to avoid thirst.

The most notable safety issue associated with chronic tolvaptan use, newly identified in Trial 156-04-251, is the potential for idiosyncratic hepatic toxicity. With a once every 4 month monitoring scheme, an imbalance in the proportion of subjects with elevated transaminases (tolvaptan > placebo) led to identification of 3 subjects (total from both Trial 156-04-251 and its open-label extension trial, 156-08-271) with laboratory and clinical evidence of potentially serious drug-induced liver injury (DILI). Based on the available data from the aforementioned trials, the sponsor proposed that appropriate subject monitoring and management be implemented to mitigate this potential risk in the ADPKD population. For this trial, standard liver parameters will be measured at baseline and then monthly thereafter.

Significant events related to glaucoma and skin neoplasms were also observed; however the causal relationship to tolvaptan remains uncertain. These adverse events (AEs) and the above attributable adverse reactions should be considered in light of the benefits of a reduced risk of ADPKD kidney complications, including renal pain, urinary tract infection, hematuria, anemia, and nephrolithiasis.¹⁰

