3.8.3.2 Treatment Discontinuation

After randomization, a subject may stop treatment permanently for a variety of reasons. Treatment discontinuations may be initiated by a subject who is not satisfied with treatment or may become medically necessary due to AEs, required treatment with a disallowed medication or therapy, or other issues, as determined by the investigator. However, each investigator must comprehensively review the circumstances and offer the subject options for continued treatment to the degree possible as described in [Section 3.8.3.4](#).

Subjects who have sustained electrolyte excursions (eg. increased serum sodium) that are considered clinically significant by the investigator and that are not able to be resolved by increasing the subject's daily water intake should be discontinued from treatment.

A subject who discontinues treatment will be recorded as an IMP discontinuation on the eCRF. They will have an EoTx visit, which should be scheduled as soon as possible after

Protocol 156-12-298

the subject's last dose of IMP to conduct the assessments defined in the Schedule of Assessments, [Table 3.7-1](#) for Phase A and [Table 3.7-2](#) for Phase B.

Subjects who discontinue IMP during Phase A, will have safety laboratory tests (including LFTs) at the 7-day posttreatment follow-up visit (see [Section 3.7.1.4.1](#)), and then will be followed every 6 months through Phase A (see Schedule of Assessments [Table 3.7-1](#)). Collection of an MRI/Ultrasound TKV measurement at the Phase A Month 12 visit will be encouraged regardless of whether the subject continues on IMP.

Subjects who discontinue IMP during Phase B, will have safety laboratory tests (including LFTs) at the 7-day posttreatment follow-up visit (see [Section 3.7.1.4.1](#)), and then will be followed every 6 months through Phase B (see Schedule of Assessments [Table 3.7-2](#)). Collection of an MRI/Ultrasound TKV measurement at the Phase B Month 12 and Phase B Month 24 visit will be encouraged regardless of whether the subject continues on IMP.

Subjects whose consents are completely withdrawn will be discontinued from the trial. These subjects' vital statuses will be collected if possible at the time points defined in [Section 3.7.4.8](#).

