9.3 Clinical Laboratory Data

Summary statistics for changes from baseline in the clinical laboratory measurements will be provided for the safety population. Potentially clinically significant results in laboratory tests identified using prospectively defined criteria will also be summarized.

According to the Food and Drug Administration (FDA) Guidance², laboratory measurements that signal the potential for drug-induced liver injury (DILI) will be reported. An incidence table and a listing will be provided for subjects who meet one or combinations of the following criteria:

- 1) ALT (alanine transaminase) or AST (aspartate transaminase) $\geq 3x$ upper limit of normal (ULN) (or baseline value for subjects with abnormal baseline)
- 2) Increase in bilirubin $\geq 2x$ ULN (or baseline value for subjects with abnormal baseline)

Protocol 156-12-298

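### SAP Appendix 1 labels serum sodium in mg/dL although its cut-points are mEq/L values, and its bands leave 145 and any decimal results between bands without a grade

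*SAP*

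**What the plan says.** SAP 9.3 commits to a summary built on fixed criteria: "Potentially clinically significant results in laboratory tests identified using prospectively defined criteria will also be summarized". Appendix 1 of the SAP carries those criteria, as one table for increases and one for decreases.

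The sodium row for increases begins "Sodium (mg/dL) Increase <145 146 - 150 151 - 155", for Grades 0 to 2 in that order, and goes on to 156 to 160 for Grade 3 and above 160 for Grade 4. The row for decreases begins "Sodium (mg/dL) Decrease <120 120-124 125-129 130-135", for Grades -4 to -1, and ends with Grade 0 at 136 or above.

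Two neighbouring rows show the style used elsewhere. Potassium reads "Potassium (mEq/L) Increase ULN >ULN-5.5 >5.5-6 >6-7 >7": the unit is mEq/L and each band opens where the last one closed. Glucose, which really is in mg/dL, reads "Glucose (mg/dL) Increase ≤ 115 >115-160 >160-250 >250-500 >500" and is joined in the same way.

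Serum sodium is drawn at the monthly safety visits in both phases, and those samples may go to a local laboratory (Protocol 3.7.1.1.6, 3.7.1.2.5 and 3.7.4.2). SAP 9.4 brings original, repeat and unscheduled results into the outlier analysis.

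**The concern.** The two sodium rows have two separate faults. The unit does not match the cut-points, and the bands do not cover every possible value. Neither is repaired elsewhere: the SAP gives no other sodium unit, no rounding rule and no rule for a result that falls in no band.

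The analyte matters. The primary objective is long-term safety. Protocol 1.3 lists "dehydration, electrolyte abnormalities, and gout" among the commonly observed risks in adults, and Protocol 3.8.3.2 gives "increased serum sodium" as its example of an electrolyte excursion. If the criterion cannot be applied as printed, whoever programs the table must choose the unit and decide what to do with 145. Fixing the criteria in advance is meant to remove that choice.

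**Working it through.** The plan states no sample size, power or other computed figure on this point, so there is nothing to reproduce. The check applies the printed bands literally.

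**Inputs.** The bands and unit come from the two sodium rows of SAP Appendix 1. Two inputs are assumptions, because the documents do not give them: an atomic mass of 22.99 for sodium, and 115 to 160 mEq/L as a generous physiological range. Sodium is monovalent, so mEq/L and mmol/L are the same number.

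**Step 1: unit.** mg/dL = mmol/L × 22.99 / 10.

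- 115 mmol/L: 115 × 22.99 / 10 = 264.4 mg/dL
- 140 mmol/L: 321.9 mg/dL
- 145 mmol/L: 333.4 mg/dL
- 160 mmol/L: 367.8 mg/dL

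All are above the Grade 4 limit of 160, and all are above 136, which is Grade 0 in the decrease table. In the other direction, 160 mg/dL is 160 × 10 / 22.99 = 69.6 mmol/L and 136 mg/dL is 59.2 mmol/L. Read literally, then, every sodium from 115 to 160 mmol/L is increase Grade 4 and none is a decrease. The assumed atomic mass is not critical: at 115 mmol/L the result would stay Grade 4 for any mass above 160 × 10 / 115 = 13.9.

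**Step 2: bands, read in mEq/L, whole numbers from 100 to 180.** In the increase table only 145 has no grade, because Grade 0 stops below 145 and Grade 1 starts at 146. In the decrease table every whole number has a grade.

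**Step 3: bands, same range, steps of 0.1.**

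- Increase: 145.0 to 145.9 (10 values), 150.1 to 150.9 (9) and 155.1 to 155.9 (9) have no grade; 10 + 9 + 9 = 28.
- Decrease: 124.1 to 124.9, 129.1 to 129.9 and 135.1 to 135.9 have no grade; 3 × 9 = 27.
- Increase Grades 3 and 4 meet at 160, so there is no gap there.

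**Step 4: what the gaps hide.** With the bands joined at the existing cut-points, 145.1 to 145.9 becomes Grade 1, 150.1 to 150.9 Grade 2 and 155.1 to 155.9 Grade 3. In the decrease table, 135.1 to 135.9 becomes Grade -1, 129.1 to 129.9 Grade -2 and 124.1 to 124.9 Grade -3. With whole numbers, if 145 is placed in Grade 0, the count of results at increase Grade 1 or higher is the same before and after joining.

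**The case against.** The strongest reply is that this is a label slip that would show itself. The cut-points fit only mEq/L, nothing tells the analyst to convert sodium to mg/dL, and a table with every subject at Grade 4 in both arms would not go unnoticed. That stands as a limit on the likely harm. It does not make the printed rule usable.

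The second reply is that the decimal gaps are conditional. The documents do not say that sodium is reported to decimals, and whole-number bands suggest that it is not. Permission to use local laboratories does not settle the matter. This also stands: the missed Grades 1 to 3 arise only if some laboratory reports decimals.

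Third, the printed <145 might be a ≤ sign lost when the PDF was read. This is weak, because ≤ and ≥ survive in other rows of the same tables. If it were so, exactly 145 would have a grade, but the unit and the decimal gaps would remain.

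Two stronger readings are tempting.

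- A reader might infer that ungraded results would be more frequent on tolvaptan, because the drug may raise sodium towards 145. The documents give no sodium mean, standard deviation or drug shift from which to show this. A result of exactly 145 is not counted as Grade 1 or higher as printed, nor once it is placed in Grade 0.
- A reader might also infer a risk to subjects, since raised sodium can lead to stopping treatment. Under Protocol 3.8.3.2 that decision rests on the investigator's judgement of sustained excursions, and Protocol 5.1 has the investigator review every laboratory result. Neither uses Appendix 1.

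Change from baseline in laboratory values is summarised separately under SAP 9.3 and needs no grade.

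**Conclusion.** The point holds, at low severity. As printed, the sodium criterion cannot be applied correctly: the unit is wrong in both rows, 145 has no increase grade, and decimal results in three intervals of each table have no grade. The unit finding rests only on the assumed atomic mass and physiological range, and is insensitive to both. The loss of Grade 1 to 3 results rests on at least one laboratory reporting decimals. If all results are whole numbers, the gap is confined to 145.

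How many results would be affected cannot be estimated from the documents, and no difference between arms is claimed. The SAP also does not say which grade counts as potentially clinically significant, so the effect on the final count cannot be stated more closely. The fault lies in a prespecified safety summary, which is why it should be corrected even though its practical effect is probably small.

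**What to change.** In both sodium rows of SAP Appendix 1, change the unit to mEq/L and join the bands at the sponsor's existing cut-points, in the style of the other rows. For example:

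- Increase: Grade 0 ≤145; Grade 1 >145-150; Grade 2 >150-155; Grade 3 >155-160; Grade 4 >160.
- Decrease: Grade 0 ≥136; Grade -1 130-<136; Grade -2 125-<130; Grade -3 120-<125; Grade -4 <120.

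The sponsor should confirm where 145 belongs, since the printed row does not say. With these bands no value is left ungraded, whatever precision a laboratory reports.

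The cost is two rows of an appendix. No data collection, analysis set or treatment rule changes.

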Appendix 2: Criteria of Potentially Clinically Significant Vital Sign Abnormalities

[figure not shown]
Test Parameters	Unit	Age	Criteria (meet either one will count)	
			Limit	Change from baseline
Heart Rate	bpm	4 - 14 Years	<= 50 >= 140	Decrease >= 15 Increase >= 15
		15 Years and older	<=50 >= 120	Decrease >= 15 Increase >= 15
SBP, Sitting	mmHg	4 – 12 Years	<=70 >= 130	Decrease >= 20 Increase>=20
		13 – 17 Years	<= 120 >= 144	Decrease >= 20 Increase>=20
DBP, Sitting	mmHg	4 – 12 Years	<= 50 >= 86	Decrease >= 15 Increase>=15
		13 – 17 Years	<= 80 >= 92	Decrease >= 15 Increase>=15

Protocol 156-12-298

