Trial Design:	
Phase A is a randomized, double-blind, placebo-controlled phase to compare tolvaptan with placebo. The duration of treatment is 12 months. It is open to subjects between the ages of 4 and 17 years, inclusive. Subjects between the ages of 12 and 17 years will be stratified by age and gender. When these stratified cohorts have been closed, enrollment for the trial will end.
 
Qualified subjects who complete Phase A may continue in Phase B. A qualified subject is defined as one who has completed Phase A on investigational medicinal product (IMP), is willing to continue in the trial, and who does not have any adverse events (AEs), which would require IMP discontinuation.
 
Phase B is an open-label phase during which qualified subjects will receive treatment with tolvaptan for 24 months.

Subject Population:	In Phase A, the required population will consist of at least 60 male and female subjects aged 12 to 17 years (inclusive), with a diagnosis of ADPKD.
	Randomization will be 1:1; tolvaptan to placebo. Subjects ages 12 to 17 will be stratified by age and gender in the following age cohorts:

- Female subjects ages 12 to 14 years, inclusive
- Female subjects ages 15 to 17 years, inclusive
- Male subjects ages 12 to 14 years, inclusive
- Male subjects ages 15 to 17 years, inclusive

The trial is also open to children between the ages of 4 to 11 years (inclusive) with ADPKD, who meet the study inclusion criteria and who, in the opinion of the investigator, would benefit from treatment. Including this latter group, the total trial population may, but is not required to, include approximately 100 subjects.

Inclusion/Exclusion Criteria:

Key Inclusion Criteria:

- Male and female subjects aged 4 to 17 years (inclusive) with a diagnosis of ADPKD as defined by the presence of family history and/or genetic criteria AND who have at least 10 renal cysts, each of which measure at least 0.5 cm, confirmed upon magnetic resonance imaging (MRI) inspection; subjects under the age of 12 years must have at least 4 cysts that are at least 1 cm in size, confirmed by ultrasound.
- Weight \geq 20 kg.
- Subjects with estimated glomerular filtration rate (eGFR) \geq 60 mL/min/1.73m² within 31 days prior to randomization (using the Schwartz formula, eGFR = 0.413 \times height [cm] /serum creatinine mg/dL).
- Independent in toileting.
- Ability to swallow a tablet.

Key Exclusion Criteria:

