Subjects may be asked to sign additional ICF/IAFs if the protocol is amended to significantly add or change procedures or if new safety information is determined.

Subjects who are not started on treatment after the ICF/IAF is signed are permitted to be rescreened under the conditions specified in [Section 3.9](#) (Screen Failures). In the event that the subject is rescreened for trial participation, a new ICF/IAF must be signed.

If a subject is legally emancipated, informed consent must be sought directly from the subject. Subjects who turn age 18 (or the age of adulthood as specified by local laws or

Protocol 156-12-298

regulations) during the trial may continue in the trial; however, must sign a new ICF at that time.

In addition to the English version of the ICF/IAF, the documents may also be translated into local languages for use in this trial. Translation with back-translation for confirmation will be utilized to ensure accuracy.

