3.3 Trial Population

The target trial population will be at least 60 male and female subjects aged 12 to 17 years (inclusive), with a diagnosis of ADPKD as defined by the presence of family history and/or genetic criteria AND who have at least 10 renal cysts, each of which measures at least 0.5 cm confirmed upon magnetic resonance imaging (MRI) inspection. In accordance with the PIP requirements, the trial will also allow subjects aged 4 to 11 years who meet criteria for entry to be enrolled concurrently during the recruitment

Protocol 156-12-298

period for the target population. It is expected that the trial may enroll approximately 100 subjects.

Subjects who are MRI-naive or under the age of 12 should have at least 4 cysts that are at least 1 cm in size confirmed by ultrasound prior to MRI inspection.

Treatment groups for the required population will be stratified by age and gender in the following age cohorts:

- Female subjects ages 12 to 14 years, inclusive
- Female subjects ages 15 to 17 years, inclusive
- Male subjects ages 12 to 14 years, inclusive
- Male subjects ages 15 to 17 years, inclusive

When > 15 subjects are enrolled in an age cohort, new screening for that age cohort will be closed; subjects concurrently in screening for that age cohort may be enrolled if they meet inclusion/exclusion criteria. When the last subject in the final age cohort for the required population has been achieved, enrollment in the trial will cease.

The trial is also open to children between the ages of 4 to 11 years (inclusive) with ADPKD, who meet the above criteria and who, in the opinion of the investigator, would benefit from treatment. Subjects, aged 4 to 11 years (inclusive), must have an ultrasound to assess renal cysts.

Qualified subjects who complete Phase A are eligible to participate in Phase B.

4 Sample Size

A sample size of at least 60 subjects from 12 to 17 years of age inclusive is proposed for the Phase A of this trial. It is expected that the trial may enroll approximately 100 subjects in total. Since the data collected will be summarized using descriptive statistics and not aimed at testing a specific hypothesis, no formal power calculations are undertaken.

5 Statistical Analysis Datasets

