9.4 Vital Sign Data

Summary statistics for changes from baseline in vital signs and potentially clinically significant results in vital signs will be summarized for the safety population. For a subject with repeat measures in either vital signs or lab tests at a visit, the last repeat will be used in the by visit summary. However, for outlier analysis (such as clinically significant abnormalities), data from all visits, no matter they are from the original visits, repeats, or unscheduled visits, will be included.

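### SAP Appendix 2 sets the low blood-pressure limits for ages 13-17 at SBP 120 and DBP 80 mmHg or below, so the safety summary would label ordinary readings as low.

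*SAP*

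**What the plan says.** SAP Appendix 2, headed "Criteria of Potentially Clinically Significant Vital Sign Abnormalities", has two age rows for sitting blood pressure. In mmHg:

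| Parameter | Age | Low limit | High limit | Change from baseline |
|---|---|---|---|---|
| SBP | 4-12 | 70 or below | 130 or above | 20 or more, either direction |
| SBP | 13-17 | 120 or below | 144 or above | 20 or more, either direction |
| DBP | 4-12 | 50 or below | 86 or above | 15 or more, either direction |
| DBP | 13-17 | 80 or below | 92 or above | 15 or more, either direction |

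The limit and change columns sit under "Criteria (meet either one will count", so an absolute value alone is enough and no fall from baseline is needed. SAP section 9.4 says that "potentially clinically significant results in vital signs will be summarized for the safety population". For outlier analysis it adds that "data from all visits, no matter they are from the original visits, repeats, or unscheduled visits, will be included". The required population in SAP section 3.3 is "at least 60 male and female subjects aged 12 to 17" years, and most of those age years fall under the 13-17 rows. Nothing elsewhere in either document explains or restricts the 13-17 low limits.

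**The concern.** Between the two age rows the low limits rise far more than the high limits, and the 13-17 low limits fall where ordinary adolescent readings would be expected. A criterion meant to pick out unusual values would then mark unremarkable ones. Long-term safety is the primary objective, and Protocol section 1.3 lists dehydration among the observed risks of tolvaptan. A low-blood-pressure table is therefore one a safety reader would look at. If most subjects in both arms carry the low flag, the table reports alarming rates and has little room to show an excess on tolvaptan.

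**Working it through.** **1. From the table alone (no assumptions)**

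- Rise in low limit from ages 4-12 to 13-17: SBP 120 − 70 = 50; DBP 80 − 50 = 30.
- Rise in high limit: SBP 144 − 130 = 14; DBP 92 − 86 = 6.
- Whole-number values left unflagged by the limits (high − low − 1):
  - SBP: 71-129 (59 values) becomes 121-143 (23 values).
  - DBP: 51-85 (35 values) becomes 81-91 (11 values).
- Example: 118/76 lies inside both unflagged ranges at age 12 and below both at age 13.
- Decrease criteria at ages 13-17:
  - An SBP fall of 20 or more from baseline b ends at b − 20 or lower. That is 120 or below whenever b is at most 140, so the criterion can add a flag only from b = 141.
  - A DBP fall of 15 or more ends at 80 or below whenever b is at most 95, so it can add a flag only from b = 96, which is already above the high limit of 92.

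**2. How often the low flag would occur (assumed distribution)**

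The SAP gives no flag rate to reproduce, and the documents give no blood-pressure distribution. The assumptions are:

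- normal readings rounded to whole mmHg, SD 10 (SBP) and 8 (DBP);
- correlation ρ = 0.5 between visits;
- k = 4 post-baseline Phase A visits with vital signs (Week 1, Months 1, 6 and 12; Protocol Table 3.7-1);
- a subject counts once if any visit is flagged;
- SBP and DBP are kept apart, because Appendix 2 lists them as separate parameters.

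With z = (limit + 0.5 − mean)/SD, the single-reading rate is Φ(z). The any-visit rate is 1 − E{[1 − Φ((z − √ρ·U)/√(1 − ρ))]^k}, with U standard normal. For example, SBP mean 115 gives z = (120.5 − 115)/10 = 0.55 and a single-reading rate of 71%. DBP mean 72 gives z = (80.5 − 72)/8 = 1.06 and 86%.

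| Parameter, mean | One reading flagged low | Any of 4 visits |
|---|---|---|
| SBP 110 | 85% | 98% |
| SBP 115 | 71% | 93% |
| SBP 120 | 52% | 82% |
| SBP 125 | 33% | 62% |
| SBP 130 | 17% | 39% |
| DBP 65 | 97% | 100% |
| DBP 72 | 86% | 98% |
| DBP 75 | 75% | 95% |
| DBP 80 | 52% | 82% |

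Varying ρ from 0.3 to 0.7 moves the any-visit share from 96% to 89% at SBP 115, from 87% to 75% at SBP 120, and from 99% to 96% at DBP 72.

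**3. Room left to show a difference**

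Suppose one arm ran 5 mmHg lower on SBP and 3 mmHg lower on DBP (assumed shifts):

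- DBP mean 72: 98.2% against 99.5%, a gap of about 1 point.
- SBP mean 115: 93% against 98%, about 5 points.
- SBP mean 120: 82% against 93%, about 12 points.
- SBP mean 125: 62% against 82%, about 19 points.

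**The case against.** The strongest reply is that the ceiling is not general. A reader might infer that the low flag is close to 100% in both arms and so carries no information. The documents do not support that:

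- They give no blood-pressure distribution. Hypertension is a listed manifestation of ADPKD (Protocol section 1), so SBP means of 120 or more are possible. There the SBP flag is well short of its ceiling and separates the arms for a 5 mmHg shift.
- Near-100% figures at every plausible mean come only from pooling low SBP with low DBP. Appendix 2 does not define such a pooled flag; its either-one rule joins limit and change.
- The 4-12 SBP limit of 70, applied to the same assumed readings, flags about 0% in both arms and would show that shift no better.

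Dilution is a further point. SAP section 9.4 summarizes the whole safety population, and the safety subgroup split in SAP section 9 is under 12 against 12 and over. Subjects aged 12 and under use the other rows, so reported arm-level rates would be lower than those above. That 13-17 covers five of the six age years in the required population does not give a share of subjects.

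On importance, this is one descriptive table, and no endpoint or hypothesis uses it. Dehydration is also followed through body weight and symptoms (Protocol section 4.2), and a data monitoring committee is in place.

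A reader might also infer that the blood-pressure rows fail for subjects who reach 18, since heart rate has a row for "15 Years and older" and Protocol section 3.4.1 lets "Subjects who turn age 18 (or the age of adulthood as specified by local laws" continue. That gap exists only if age at visit selects the row, which the SAP does not state. Under baseline age there is none, so it is a side question.

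All of these objections stand as limits on size and weight. None explains the 13-17 low limits or the redundancy they create.

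**Conclusion.** The 13-17 low limits are wrong as written, in the sense that they conflict with the 4-12 rows and with the table's own decrease criteria. That conclusion needs no assumed data. The summary would label ordinary readings as low in both arms.

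How close the flag comes to its ceiling depends on the distribution assumed above. It is near the ceiling for DBP at means of about 72 or lower and for SBP at means of about 115 or lower, but not for SBP at higher means. The figures apply to 13-17 year-olds only.

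Mean changes from baseline (SAP section 9.4) and the adverse-event tables (SAP section 9.2) are unaffected. The correction should be made, but the defect does not threaten the trial's endpoints. The documents do not show which limits were intended, and this review proposes none.

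**What to change.** Check the 13-17 low limits of 120 and 80 against their source. Reconcile them with the 4-12 rows and the change criteria, and correct Appendix 2 and the matching programming constants, with the values set by the sponsor. Protocol Amendment 2 records that Phase A assessments were complete by then, and an interim report was planned from the Phase A snapshot. If the Phase A outlier table has already been produced, it should be re-run with the corrected limits.

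The cost is one SAP table, a few constants and possibly one re-run. No new data are needed.
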